In order to help clarify current treatment of severe thrombocytopenia in preterm neonates and provide baseline information for a clinical trial, we carried out the first prospective study of neonatal platelet transfusion practices (PlaNeT-1 study, Stanworth et al, 2009), in which we collected detailed information both about indications for transfusion and outcome (including bleeding). In this study we observed platelet transfusion practices in 7 UK neonatal centres. 169 neonates with platelet counts of  $<60 \times 10^9/L$  were enrolled in this study. In this study, major haemorrhage occurred in 13% of severely thrombocytopenic neonates (intraventricular haemorrhage 53%, pulmonary 26%, renal 11%, 'other' 10%), the vast majority (84%) of neonates who had a major haemorrhage were  $<30$  weeks gestation at birth. The study confirmed previous data that sepsis and necrotising enterocolitis (NEC) are common underlying diagnoses in thrombocytopenic neonates who bleed. In contrast, neonates with thrombocytopenia secondary to intra uterine growth retardation or pregnancy-induced hypertension tend not to have major haemorrhage despite severe thrombocytopenia. There was no clear relationship between major bleeding and platelet counts in the PlaNeT-1 study (Stanworth et al, 2009), and further analysis of all bleeding events (including minor bleeds) indicates no evidence for a significant increase in rates of bleeding with severe thrombocytopenia (data unpublished; manuscript in preparation). Data from the PlaNeT-1 study also showed that 69% of all neonates with a platelet count below  $60 \times 10^9/L$  were given a platelet transfusion. The findings in PlaNeT-1 (platelet thresholds for transfusion illustrated in Figure 1) highlighted the clinical uncertainty and variation in practice but also provided information about the thresholds in place at those NICU's who have indicated a willingness to participate in this trial.

Recent randomised trials addressing red cell transfusion triggers for anaemic neonates (Bell et al 2005 and Kirpalani et al 2006) have contributed to the debate on appropriate neonatal red cell transfusions. However, a comparable platelet trigger trial, assessing clinically relevant outcomes, has never been undertaken in preterm neonates with severe thrombocytopenia (platelet counts  $<50 \times 10^9/L$ ).

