### 5.2 Details of Registration Process and Randomisation

1. The local PI (or designate) will be responsible for identifying and consenting the parents/guardians of eligible neonates once the platelet count has dropped to  $<100 \times 10^9/L$ .
2. A screening sheet with a log number will be completed on all neonates admitted to selected participating units with platelets  $<100 \times 10^9/L$  and GA  $<34$  weeks. The log will include GA, post-natal age, birth weight and main diagnosis. It will include neonates not approached, and those neonates approached but in whom consent was not obtained for the trial (with reasons) and therefore will define how representative randomised neonates are as a group relative to the group of eligible neonates who were not randomised.
3. Eligibility for randomisation will be assessed with reference to inclusion and exclusion criteria.
4. When the neonate's platelet count falls to  $<50 \times 10^9/L$ , the PI or designate (the randomiser) will ensure a cranial ultrasound has been undertaken within the last 6 hours, and will then complete the trial registration/randomisation form and access the web based randomisation service at <http://www.sealedenvelope.com> to obtain a unique trial number and assignment of treatment policy. Before logging onto the website to randomise the neonate, the following pieces of information must be available: the neonate's gestational age at birth (in weeks and days); knowledge of presence or absence of IUGR; the most recent platelet count (which must be below  $50 \times 10^9/L$ ) and the date and time of the most recent cranial USS, which must have been undertaken within 6 hours before randomisation.
5. Following randomisation, the randomisation service will e-mail confirmation of the allocated treatment policy and trial number to the PI and Trial Manager. The PI will place the emailed allocated treatment policy in the neonate's medical notes.
6. The local PI/designate is responsible for informing the neonate's consultant and the parents of the neonate's treatment allocation, and for placing a label indicating trial participation on the cot and cover of the neonate's medical notes.

7. The local PI/designate will complete the patient's screening sheet adding the patient's trial number to the existing data. The local PI/designate will also be responsible for informing the Blood Bank of the trial number and the trial treatment allocation.

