### 7.4 Randomisation

Background data will be collected before or at the time of randomisation including:

- gestational age at birth
- weight at birth
- gender
- postnatal age in days
- weight at enrolment
- co-existing or prior medical conditions/ diagnosis including major bleeds, IUGR, NEC  $\geq$  Stage 2 defined as per Bell's criteria (Bell et al; 1978) and sepsis

Once final eligibility is confirmed, the neonate will be randomised into the study according to the procedures described in Section 5

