### **9.2.2 Secondary outcomes**

Secondary outcomes include:

- Proportion of patients surviving to go home following a major bleed, censoring at discharge
- Proportion of patients surviving to go home without having had a major bleed, censoring at discharge
- Proportion of patients who have died up to study day 28
- Proportion of patients who sustain a major bleed up to study day 28
- The rate and time from randomisation of minor, moderate and major bleeding derived from the bleeding assessment tool up to study day 14, and for major bleeds up to study day 28. Definitions for all grades of bleeds are shown in the bleeding assessment tool; grading will be assigned based on a modified version of the WHO Bleeding Score
- Number of platelet units transfused up to study day 28
- Time to discharge home, censoring on death
- Neuro-developmental outcome as assessed by the Thames Regional Perinatal Outcome Group/ Standard Electronic Neonatal Database/ National Neonatal Audit Programme (TRPG/SEND/NNAP) 2- year corrected age outcome form at 2 years corrected postnatal age. This will provide a basis of correlation with the WHO functional disability score.
- Platelet transfusion-related adverse events from the time of randomisation up to end of study (section 7.6 and 8.3.2)

A comprehensive statistical analysis plan will be written before the final data analysis is conducted. Analysis of all outcomes will be conducted on the basis of intention to treat. The primary analysis will be adjusted for the stratifying variables.

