### 9.3 Sample size

This trial (PlaNeT-2) represents the first trial in the field of neonatal platelet transfusion prophylaxis in this population of preterm neonates. This study has been designed as a two stage trial with an interim analysis which will inform the final sample size requirement and trial feasibility (See Section 9.4). Data on the frequency of bleeding outcomes in severely thrombocytopenic neonates is available from the PlaNeT-1 survey (Stanworth et al, 2009), in which 30/169 or 18% of neonates died or experienced a major bleed while on study. However, this proportion applies to neonates of all gestational ages, and only during episodes of significant thrombocytopenia. Overall mortality (and new major bleeds) is likely to be greater than this figure derived from PlaNeT-1 data for the baseline event rate in the arm A of this trial. Assuming a proportion of 20% for the primary outcome for Arm A, in order to detect a difference between proportions of 8% (assuming that the proportion in Arm B is 12%), using a two-sided test, 5% significance level and 80% power, 329 neonates in each group is needed. Rounding this figure up, a total of 660 neonates will be required for this study. Note that this calculation does not take account of withdrawals or loss to follow-up.

The Data Monitoring Committee (DMC) will be closely monitoring the primary outcome (mortality and major bleeds) as well as safety data for any imbalance between the two arms (See Sections 10, 11 for further details).

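### Baseline sepsis and NEC are recorded and linked to bleeding by the protocol, but probably sit outside the primary model; adding them would bring a modest gain in precision

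*Protocol*

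**What the plan says.** Four places in the protocol bear on this.

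- **Section 2.1** summarises the earlier observational study: "sepsis and necrotising enterocolitis (NEC) are common underlying diagnoses in thrombocytopenic neonates who bleed". It contrasts these infants with those whose thrombocytopenia follows growth restriction or pregnancy-induced hypertension, who tended not to have major haemorrhage. It found no clear relationship between platelet count and major bleeding.
- **Section 7.4** lists the background data taken before or at randomisation: "co-existing or prior medical conditions/ diagnosis including major bleeds, IUGR, NEC" of stage 2 or above, and sepsis.
- **Section 5.2** lists what must be to hand before logging on to randomise: "the neonate's gestational age at birth (in weeks and days); knowledge of presence or absence of IUGR", together with the latest platelet count and the time of the cranial scan. Sepsis and NEC are not on that list. Section 9.1 says that allocation is by minimisation with a random element and names no factors.
- **Section 9.2.2** states: "The primary analysis will be adjusted for the stratifying variables". It does not list those variables, and it refers to a statistical analysis plan still to be written.

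**The concern.** The protocol's own planning data tie bleeding to the underlying diagnosis. The imaging rule in section 9.2.1 points the same way: proven sepsis or NEC that required blood products stops the trial team from assuming that no major bleed occurred. The factor is known at entry and is plausibly prognostic for the primary composite, yet the stated model would probably leave it out.

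Two things are at stake. A prognostic covariate left out of the model gives up some precision. And if the arms differ by chance in the share of infants with sepsis or NEC, that difference stays in the main estimate. The trial is open: section 5.2 has the consultant, the parents and the blood bank told of the allocation. A covariate added only after an imbalance has been seen would look data-driven, so it is better fixed in advance.

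**Working it through.** **1. The plan's own figure.** The inputs are from section 9.3: "Assuming a proportion of 20% for the primary outcome for Arm A", 12% in Arm B, and "using a two-sided test, 5% significance level and 80% power, 329 neonates in each group is needed". With the pooled-variance formula and no continuity correction:

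n = [1.96·√(2·0.16·0.84) + 0.8416·√(0.20·0.80 + 0.12·0.88)]² / 0.08² = (1.016 + 0.434)² / 0.0064 = 328.5, rounded up to 329 per arm.

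This matches the protocol. At 330 per arm (660 in total) power is 80.2%.

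**2. Inputs that the documents do not give.** Neither the prevalence of sepsis or NEC at entry nor its odds ratio for the primary outcome is stated. Both are assumptions here: prevalence 30-50% with an odds ratio of 2 to 5, and in a second check prevalence 20-60% with an odds ratio of 1.5 to 3.

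**3. Effect of a chance imbalance on the estimate.** With simple 1:1 allocation of 660 infants, the between-arm difference in prevalence p has SD √(4p(1−p)/660). An imbalance of 1.96 SD shifts the unadjusted event difference by that amount times the risk difference between infants with and without the factor, with Arm A held at 20% overall.

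Example, p = 0.3 and odds ratio 3:

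- Risks are 1/7 without the factor and 1/3 with it. Check: 0.7 × 1/7 + 0.3 × 1/3 = 0.20, and the odds are 1/6 and 1/2.
- The risk difference is 0.190.
- The SD is √(0.84/660) = 0.0357, and 1.96 × 0.0357 = 0.070.
- The shift is 0.070 × 0.190 = 0.013, or 1.3 points.

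| Prevalence | OR 2 | OR 3 | OR 5 |
|---|---|---|---|
| 30% | 0.8 | 1.3 | 2.0 |
| 50% | 0.8 | 1.3 | 1.8 |

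These are percentage points, against a target difference of 8. The second range gives 0.4 to 1.3 points. An imbalance this large or larger, in either direction, is expected about 1 time in 20.

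**4. Type I error.** Logistic regression was simulated with 330 per arm and 6,000 runs per scenario over the second range. The rejection rate under no effect was 4.7-5.4% without the covariate and 4.8-5.3% with it. The simulation standard error is √(0.05·0.95/6000) = 0.3 points, so both are compatible with 5%.

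**5. Power against an unadjusted model.** From 1,500 simulated trials per cell (without / with the covariate, %):

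| Prevalence | OR 2 | OR 3 | OR 5 |
|---|---|---|---|
| 30% | 80.1 / 81.1 | 82.5 / 82.9 | 82.5 / 85.0 |
| 50% | 81.1 / 80.9 | 79.1 / 80.5 | 80.9 / 82.9 |

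Each figure has a standard error of about √(0.8·0.2/1500) = 1 point. The 6,000-run check over the second range gave a change of about 0 to +1.5 points.

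**6. Power against the comparator closer to the plan.** The planned model already holds the stratifying variables. Taking these to be gestation and growth restriction, with assumed effects, and letting them either overlap or not overlap with sepsis/NEC, the covariate added about 0 to +2 points at an odds ratio of 2 to 3, and about +2.5 to +4 at 5.

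**The case against.** The strongest reply is that the choice of further covariates belongs in the statistical analysis plan, and that adjusting for the stratifying variables is standard and defensible. That is largely right. What remains is that section 9.2.2 does commit to a covariate set, so the suggestion changes a stated method and does not ask for missing detail.

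Three stronger readings are tempting, and the document supports none of them.

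- A reader might infer that the protocol adjusts only for the stratifying variables and so excludes sepsis and NEC. It does not say so. The variables are never named, and their content is inferred from a log-on list that also serves eligibility checks.
- A reader might take sepsis and NEC to be the main cause of thrombocytopenia, or established strong predictors of both death and bleeding. Section 2.1 says only that they are common among infants who bleed. It gives no risk ratio and does not link them to death. Its one quantified association is gestation: 84% of infants with major haemorrhage were below 30 weeks.
- A reader might call the unadjusted result biased. Chance imbalance under randomisation is not bias. It is already reflected in the standard error, and the type I error check confirms this.

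It can also be said that gestation and growth restriction, if they are minimisation factors, already cover part of the prognostic information. They do, but infants without growth restriction still mix several causes, and step 6 shows that a gain can remain.

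A practical objection also stands in part. Section 7.13 and Appendix B define culture-negative sepsis by antibiotics actually given for at least five days, which may not be known at entry. Section 8.4 defines it by the course intended. The covariate must follow the latter, or information from after randomisation would enter the model.

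**Conclusion.** The point holds as a low-cost improvement. The planned primary test is valid as it stands. Adding baseline sepsis/NEC would bring about 0 to +2 points of power for an odds ratio of 2 to 3, and up to about +4 for 5, at 30-50% prevalence. It would also remove from the estimate a possible shift of about 0.8 to 2.0 points under a 1-in-20 imbalance.

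These sizes rest on assumed prevalence, odds ratios and stratifying-variable effects, and on simple 1:1 allocation. Minimisation on factors correlated with sepsis/NEC would make the imbalance smaller. If the unnamed stratifying variables turn out to include sepsis or NEC, nothing needs to change.

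**What to change.** In section 9.2.2, beside the stratifying variables, add one prespecified covariate to the primary model: NEC stage 2 or above, or sepsis, diagnosed by the time of randomisation (yes/no, from the section 7.4 baseline form). State that culture-negative sepsis counts by the course of antibiotics planned at randomisation and not by the days later completed. Report the result without this covariate as a sensitivity analysis.

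The cost is one more model term. The data are already collected and the 660 stands. The gain may be near zero if the factor is only weakly prognostic. If the model is logistic, the odds ratios with and without the covariate are different quantities and will not agree exactly even with perfect balance, which the report should say.

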### **2.1.1 Principal clinical research question being addressed**

Is a prophylactic platelet transfusion policy for preterm neonates based on a higher threshold blood platelet count of  $<50 \times 10^9/L$  superior to one based on a lower threshold platelet count of  $<25 \times 10^9/L$  with regard to mortality and major bleed events as measured up to Study day 28 after randomisation?

[figure not shown]
## **2.2 Justification for platelet count thresholds in this randomised trial**

The justification for selection of lower and higher platelet count thresholds at  $25 \times 10^9/L$  and  $50 \times 10^9/L$  for this trial is based on:

1. Current national guidance (BCSH 2004 Handbook of Transfusion Medicine, 2007) recommends platelet transfusion thresholds of  $20-30 \times 10^9/L$  and  $50 \times 10^9/L$  for neonates depending on the clinical situation.
2. In a UK survey, the most common stated thresholds for transfusion were 25 and  $30 \times 10^9/L$  in well infants at term and preterm, respectively (Chaudhary et al, 2009).
3. In PlaNet-1 most transfusions were given at platelet counts between 10 and  $50 \times 10^9/L$  (see histogram below). The 50th and 90th centile pre-transfusion platelet count thresholds observed in the PlaNeT-1 study were 27 and  $48 \times 10^9/L$ .
4. In PlaNeT-1, 173 /415 (42%) transfusions were administered at a minimum platelet count of  $<25 \times 10^9 /L$ , and 383/415 (92%) transfusions were administered at a minimum platelet count of  $<50 \times 10^9/L$ , so there should be clear difference in the intervention between the two arms of this proposed trial
5. The recognition that in the only randomised controlled trial to assess a threshold level for the effectiveness of neonatal prophylactic platelet transfusions, the lower platelet count threshold was  $50 \times 10^9/L$  (Andrew et al, 1993).

The figure below shows the variation of platelet count threshold used for transfusion in the PlaNeT-1 study. This was an observational study and decision to administer a platelet transfusion was at the discretion of the attending clinician.

**Figure 2.0 Lowest Platelet Count ( $\times 10^9$  /L) recorded prior to Transfusion in the PlaNeT-1 Study**

The above graph has been truncated to exclude 1 out of 415 transfusions where the platelet count was  $266 \times 10^9$ /L but the neonate was given a transfusion due to its clinical condition.

## **3 SELECTION OF CENTRES/CLINICIANS**

### **3.1 Centre/Clinician eligibility criteria**

Centre selection will be based on relevant clinical and research infrastructure, adequate resources and facilities to support recruitment, and adequate qualified staff to conduct the trial properly and safely. Centres are required to have the facility and expertise to perform cranial ultrasound scans around the clock. Centres are expected to care for neonates providing intensive and high dependency care as per British Association of Perinatal Medicine (BAPM) (2001). The TMG will invite eligible centres and will discuss the resources required for conducting the trial, including the importance of training and education to the clinical staff on the use of the bleeding assessment tool.

All UK laboratories should be Clinical Pathology Accreditation accredited, and National External Quality Assurance Scheme participants.

The trial will start at the centres listed in section 18. Additional trial centres across the UK will be approached as required once the trial is successfully up and running at the initial centres.

## 4 SELECTION OF NEONATES AND CONSENTING

Neonates will be identified by the research team at trial centres and assessed as to their eligibility to enter the trial according to the criteria below. Identification and counselling of parents/guardians will start when the platelet count falls below  $100 \times 10^9/L$ . A trial screening log will be completed for all neonates admitted to selected participating units with platelets  $<100 \times 10^9/L$  and gestational age (GA)  $<34$  weeks. This will record data such as GA, post-natal age, gender and main diagnosis. The log will include neonates not approached, and those neonates approached but in whom consent was not obtained for the trial (with reasons) and will define how representative randomised neonates are as a group relative to the group of eligible neonates who were not randomised.

### 4.1 Obtaining Consent

Parents/ guardians will be counselled when the platelet count is below  $100 \times 10^9/L$ . At this stage a Parent Information Leaflet will be provided. Written, informed consent will be obtained. As part of the consent process, it will be explained to the parents/ guardians that randomisation will occur only if the platelet count falls below  $50 \times 10^9/L$ . It is estimated that platelet count will drop to below  $50 \times 10^9/L$  in about 50% of neonates with platelet counts below  $100 \times 10^9/L$ . If the baby's platelet count does not drop to below  $50 \times 10^9/L$  they will not be randomised and will not participate in the study.

For neonates with an initial platelet count of  $<50 \times 10^9/L$ , parents will be approached for consideration of immediate study participation.

### 4.2 Patient inclusion criteria for randomisation

1. Written informed consent obtained
2. Admission to a participating NICU (includes postnatal transfers)
3.  $<34$  weeks gestational age at birth
4. A platelet count of  $<50 \times 10^9/L$
5. Cranial ultrasound scan must have been undertaken less than 6 hours prior to randomisation in order to rule out recent major Intraventricular Hemorrhage (IVH) (refer to section 6.4 )

### 4.3 Patient exclusion criteria for randomisation

1. Major/life-threatening congenital malformations (e.g. chromosomal anomalies, Fanconi's anaemia, Thrombocytopenia Absent Radius syndrome).
2. The occurrence of a major/ severe bleed within the previous 72 hours. However, the neonate may be eligible for randomisation later, once 72 hours has elapsed, provided there are no further major bleeds and the baby meets all the inclusion criteria (refer to Section 6.4)
3. All foetal intracranial haemorrhages excluding subependymal haemorrhage from any antenatal ultrasound scan.
4. Known immune thrombocytopenia or family history of alloimmune thrombocytopenia or maternal antiplatelet antibodies or maternal idiopathic thrombocytopenic purpura.
5. Neonates judged by the attending neonatologist to be unlikely to survive more than a few hours at the time of proposed randomisation.
6. Neonates who were *not* given parenteral Vitamin K after birth.

### 4.4 Co-Enrolment

Participation in other neonatal clinical studies is permitted as long as the other studies do not influence the outcomes or end points or compromise the overall study design and delivery of the Planet 2 study.

Babies randomised to the Planet 2 study could also be enrolled in studies such as Baby OSCAR, PREVAIL, PINE and ELFIN as long as the Chief Investigators for these studies are happy with this.

